### **4.3.3 Investigational Medicinal Product Accountability**

All IMPs required for completion of this study (obinutuzumab, rituximab, idasanutlin, and venetoclax) will be provided by the Sponsor. The study site will acknowledge receipt of IMPs using the IxRS to confirm the shipment condition and content. Any damaged shipments will be replaced.

IMPs either will be disposed of at the study site according to the study site's institutional standard operating procedure or will be returned to the Sponsor with the appropriate documentation. The site's method of IMP destruction must be agreed to by the Sponsor. The site must obtain written authorization from the Sponsor before any IMP is destroyed, and IMP destruction must be documented on the appropriate form.

Accurate records of all IMPs received at, dispensed from, returned to, and disposed of by the study site should be recorded in the Drug Inventory Log.

### **4.3.4 Post-Trial Access to Obinutuzumab, Rituximab, Idasanutlin, and Venetoclax**

Currently, the Sponsor does not have any plans to provide obinutuzumab, rituximab, idasanutlin, venetoclax, or any other study treatments or interventions to patients who have completed the study. The Sponsor may evaluate whether to continue providing obinutuzumab, rituximab, idasanutlin, and venetoclax in accordance with the Roche Global Policy on Continued Access to Investigational Medicinal Product, available at the following Web site:

[http://www.roche.com/policy\\_continued\\_access\\_to\\_investigational\\_medicines.pdf](http://www.roche.com/policy_continued_access_to_investigational_medicines.pdf)

## **4.4 CONCOMITANT THERAPY**

Concomitant therapy includes any medication (e.g., prescription drugs, over-the-counter drugs, herbal or homeopathic remedies, nutritional supplements) used by a patient from 14 days prior to the screening period to the visit at the EOI or at the end of post-induction treatment, whichever occurs later. All such medications should be reported to the investigator and recorded on the Concomitant Medications eCRF.

### **4.4.1 Permitted Therapy**

Premedication is permitted as described in Section [4.3.2.5](#).

Patients who use oral contraceptives, hormone-replacement therapy, or other maintenance therapy should continue their use.

Hematopoietic growth factors are allowed in *all study phases* if clinically indicated and used in accordance with the prescribing information. *G-CSF may be used in the DLT period (Cycles 1 and 2) to treat Grade  $\geq 3$  neutropenia, but is not allowed as prophylaxis. Outside of the DLT observation window during the dose-escalation phase and during the expansion phase, G-CSF may be administered in each cycle of therapy*

as primary prophylaxis for neutropenia, according to the American Society of Clinical Oncology (ASCO), EORTC, and European Society for Medical Oncology (ESMO) guidelines ([Smith et al. 2006](#)) or according to each site's institutional standards.

Prophylactic treatment with antibiotics should be administered as per standard practice.

Necessary supportive measures for optimal medical care will be given throughout the study according to institutional standards.

#### **4.4.2 Prohibited and Cautionary Therapy**

Use of the following therapies (excluding protocol-specified treatments) is prohibited during the study:

- Any anti-cancer therapy, approved or investigational, other than intrathecal central nervous system prophylaxis
- Hormonal therapy other than contraceptives, stable hormone-replacement therapy, or megestrol acetate
- Biologic agents other than hematopoietic growth factors (as described in Section [4.4.1](#))
- Vaccination with live vaccines is not recommended during treatment with obinutuzumab or rituximab and until B-cell recovery

MDM2 antagonists were shown in vitro to affect all types of hematopoietic progenitors, including megakaryocytic differentiation. They inhibit both early and late stages of megakaryopoiesis, including ploidy and proplatelet formation ([Mahfoudhi et al. 2016](#)). As a consequence, the effect on early progenitors might induce long-lasting thrombocytopenia in vivo.

Therefore, because of the potential severity and duration of thrombocytopenia induced by study treatment, patients in clinical need for chronic treatment with oral or parenteral anticoagulant/antiplatelet agents (e.g., warfarin, chronic daily treatment with aspirin [ $> 325$  mg/day], clopidogrel, dabigatran, apixaban, rivaroxaban, systemic LMWH, or subcutaneous anticoagulant prophylaxis) are excluded from this study. For patients considered eligible for the study because they are able to tolerate interruption of anticoagulant or antiplatelet treatment, these agents must be discontinued 7 days (or 5 half-lives, whichever is shorter) prior to initiating study treatment (except used as flushes for indwelling catheters). After the study treatment completion or discontinuation visit, treatment with anticoagulant/antiplatelet agents may be re-initiated for patients with transfusion-independent adequate platelet levels as clinically indicated.

Idasanutlin is metabolized mainly by multiple pathways such as CYP3A, CYP2C8, and UGT (UDP glucuronosyltransferase) enzymes. Due to the fact that idasanutlin PK exposure is only minimally changed during treatment with a strong CYP3A inhibitor posaconazole as summarized in Section [1.3.2.1](#), it is not a sensitive CYP3A or CYP2C8

substrate and thus its metabolism may only be affected by concomitant CYP3A or CYP2C8 inducers. Venetoclax is metabolized by CYP3A4 and CYP3A5 enzymes and is a P-glycoprotein and BCRP substrate; metabolism may be affected by concomitant CYP3A inhibitors and inducers, or P-glycoprotein inhibitors. Idasanutlin M4 metabolite and venetoclax are organic anion-transporting polypeptide (OATP)-1B1/3 transporter inhibitors that may affect concomitant OATP1B1/3 substrates. Idasanutlin inhibits CYP2C8 metabolism, which may affect concomitant CYP2C8 substrates. Venetoclax inhibits P-glycoprotein and BCRP, which may affect concomitant P-glycoprotein and BCRP substrates. Thus, in order to prevent undesirable DDIs during the study, the use of any of the medications listed in [Table 8](#) (CYP2C8 substrates) and [Table 10](#) (OATP1B1/3 substrates) is prohibited, while the use of any of the medications listed in [Table 9](#) (strong and moderate CYP3A inhibitors and inducers) is either prohibited within the DLT evaluation window (first two cycles in the escalation phase) or allowed after the DLT evaluation window after being washed out in sufficient duration (for inhibitors) or concomitant use with caution (for inducers). Note that gemfibrozil is also a potent UGT1A3 inhibitor that will be excluded from use in this study. Medications listed in [Table 11](#) should be used with caution because of potential DDIs with venetoclax.

The UGT1A3 inhibitor gemfibrozil, the CYP2C8 substrates listed in [Table 8](#), the CYP3A inhibitors and moderate CYP3A inducers listed in [Table 9](#), and the OATP1B1/3 substrates listed in [Table 10](#) must be discontinued 7 days prior to start of study treatment. Strong CYP3A inducers listed in [Table 9](#) must be discontinued 14 days prior to the start of study treatment.

**Table 8 Prohibited CYP2C8 Substrates**

Substrates
Amiodarone
Amodiaquine
Cerivastatin
Chloroquine
Ibuprofen
Lovastatin
Montelukast
Paclitaxel
Pioglitazone
Repaglinide
Rosiglitazone
Simvastatin
Toresamide

**Table 9 Examples of Strong and Moderate CYP3A Inhibitors and Inducers**

CYP3A Inhibitors		CYP3A Inducers	
Strong a	Moderate b	Strong c	Moderate c
boceprevir	aprepitant	carbamazepine	bosentan
clarithromycin	cimetidine	enzalutamine	efavirenz
cobicistat	ciprofloxacin	mitotane	etravirine
conivaptan	clotrimazole	phenytoin	modafinil
		rifampin	
danoprevir/ritonavir	crizotinib d	St. John's wort	
diltiazem	cyclosporine d		
elvitegravir/ritonavir	dronedarone		
idelalisib d	erythromycin		
indinavir	fluconazole		
itraconazole	fluvoxamine		
ketoconazole	imatinib d		
lopinavir/ritonavir	tofisopam		
nefazodone	verapamil		
nelfinavir			
ritonavir			
paritaprevir/ritonavir combinations			
posaconazole			
saquinavir/ritonavir			
telaprevir			
tipranavir/ritonavir			
troleandomycin			
voriconazole			

a Concomitant use of venetoclax with strong CYP3A inhibitors is to be avoided to prevent venetoclax exposure elevation with potentially increased toxicities; use an alternative medication that is not an inhibitor. If must be used medically, they are allowed during the study only if the patient has completed the DLT evaluation window (if patient is in a dose escalation cohort) and venetoclax is withheld in that cycle. After discontinuation of the strong CYP3A inhibitor, wait for 7 days before restarting venetoclax treatment. As obinutuzumab and idasanutlin (not a sensitive CYP3A substrate with regard to CYP3A inhibition) PK exposures are not expected to be affected from CYP3A inhibition, their dosing schedules should continue in 28-d cycles if venetoclax has to be withheld in the study.

b Concomitant use of venetoclax with moderate CYP3A inhibitors is to be avoided to prevent venetoclax exposure elevation with potentially increased toxicities; use an alternative medication that is not an inhibitor. If must be used medically, they are allowed during the study only if the patient has completed the DLT evaluation window (if patient is in a dose escalation cohort) and a 50% dose reduction for venetoclax is implemented in that cycle. After discontinuation of the moderate CYP3A inhibitor, wait for 3 days before increasing venetoclax back to the initial dose

**Table 9 Examples of Strong and Moderate CYP3A Inhibitors and Inducers (cont.)**

- c Concomitant use of venetoclax and idasanutlin with strong or moderate CYP3A inducers is to be avoided to prevent venetoclax and idasanutlin exposure loss compromising efficacy; consider alternative medications. If the patient requires use of these medications, use with caution and contact Roche Medical Monitor (refer to Section 5.4.1) for guidance. The inducers are allowed during the study only if the patient has completed the DLT evaluation window (if patient is in a dose escalation cohort).
- d These are anti-cancer agents; consult with the Medical Monitor before use.

**Table 10 Prohibited OATP1B1/3 Substrates**

OATP1B1/3 Substrates a
Asunaprevir
Atorvastatin
Atrasentan
Bosentan
Cerivastatin
Danoprevir
Docetaxel
Ezetimibe
Fexofenadine
Fluvastatin
Glyburide
Irinotecan
Nateglinide
Olmesartan
Paclitaxel
Pitavastatin
Pravastatin
Repaglinide
Rifampin
Rosuvastatin
Simvastatin acid
Telmisartan
Valsartan

- a OATP1B1/3 substrates with  $t_{1/2}$  shorter than 1 day are allowed, except during idasanutlin treatment and for 72 hours after the last dose of idasanutlin.

**Table 11 Cautionary Medications for Venetoclax**

CYP3A		P-Glycoprotein	
Weak Inhibitors	Weak Inducers	Substrates	Inhibitors
alprazolam amiodarone amlodipine bicalutamide a chlorzoxazone cilostazol cimetidine fluoxetine fosaprepitant ginkgo goldenseal isoniazid istradefylline ivacaftor lomitapide nilotinib a oral contraceptives pazopanib a ranitidine ranolazine tacrolimus tipranavir/ritonavir ticagrelor zileuton	amprenavir aprepitant armodafinil clobazamechin acea prednisone rufinamide vemurafenib a	aliskiren ambrisentan colchicine dabigatran etexilate digoxin everolimus a fexofenadine lapatinib a loperamide maraviroc nilotinib a ranolazine saxagliptin sirolimus a sitagliptin talinolol tolvaptan topotecan a	amiodarone azithromycin captopril carvedilol dronedarone felodipine propafenone quinidine ranolazine ticagrelor
BCRP			
Substrates		Inhibitors	
methotrexate a mitoxantrone a lapatinib a sulfasalazine topotecan a		gefitinib a	

a These are anti-cancer agents; consult with the Medical Monitor before use.

The lists of medications are not necessarily comprehensive. Thus, the investigator should consult the prescribing information for any concomitant medication as well as the Internet references provided below when determining whether a certain medication

should be inhibited by the above rationale. In addition, the investigator should contact the Medical Monitor if questions arise regarding any medications not listed above.

<http://www.fda.gov/Drugs/DevelopmentApprovalProcess/DevelopmentResources/DrugInteractionsLabeling/ucm093664.htm>

<http://medicine.iupui.edu/clinpharm/ddis/table.aspx>

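### Cimetidine and tipranavir/ritonavir are classed as moderate and strong CYP3A inhibitors in Protocol Table 9 but as weak ones in Table 11, with different venetoclax instructions; Table 9 is the natural governing rule and the Table 11 entries should go

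*Protocol*

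**What the plan says.** Section 4.4.2 of the Protocol sorts interacting medicines into Tables 8 to 11. Two of these tables matter here.

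- **Table 9, strong and moderate CYP3A inhibitors.** Cimetidine stands in the moderate column and tipranavir/ritonavir in the strong column. The footnotes say that both classes are to be avoided "to prevent venetoclax exposure elevation with potentially increased toxicities". If a strong inhibitor is medically necessary, footnote a allows it only when "venetoclax is withheld in that cycle", with a 7-day wait before restart. For a moderate inhibitor, footnote b requires that "a 50% dose reduction for venetoclax is implemented in that cycle", with a 3-day wait before the initial dose is resumed. Both footnotes bar use before the DLT window is complete, but only for patients in a dose-escalation cohort.
- **Table 11, cautionary medicines for venetoclax.** The weak CYP3A inhibitor column contains both drugs, in the runs "chlorzoxazone cilostazol cimetidine fluoxetine fosaprepitant" and "tacrolimus tipranavir/ritonavir ticagrelor zileuton". The body text says that Table 11 medicines "should be used with caution because of potential DDIs with venetoclax". It gives no dose rule, no DLT-window bar and no washout for them.

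The body text also says that use of the medicines listed in Table 9 "is either prohibited within the DLT evaluation window (first two cycles in the escalation phase) or allowed after the DLT evaluation window", and that the CYP3A inhibitors listed there "must be discontinued 7 days prior to start of study treatment".

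**The concern.** A drug cannot be both a weak and a moderate (or strong) inhibitor of the same enzyme, so one of the two listings is wrong for each of these drugs. The two listings also lead to different handling of venetoclax.

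A site that looked up cimetidine only in Table 11 could give it alongside full-dose venetoclax. Table 9 asks for avoidance, or a halved dose where avoidance is not possible, and gives raised venetoclax exposure as the reason.

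The class also matters at entry. The exclusion criterion on recent CYP3A inhibitors (Section 4.1.2) names strong and moderate inhibitors and does not point to Table 9. Cimetidine taken in the 7 days before first dosing is caught by that criterion under its Table 9 class, but not under its Table 11 class.

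Nothing in Sections 4.4.1 to 4.4.3, the table footnotes or the exclusion criteria says which listing prevails. The closing advice after Table 11 refers sites to prescribing information and websites. It refers them to the Medical Monitor for medicines that are not listed, whereas these two are listed twice.

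**Working it through.** The plan states no figure on this point, so the check is a comparison of lists and instructions.

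**Step 1: the lists.** Table 9 holds 22 strong and 13 moderate inhibitor entries, 22 + 13 = 35. The weak CYP3A inhibitor column of Table 11 holds 24 entries. The names common to both are cimetidine and tipranavir/ritonavir: 2 of 24, or 2 of 35.

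**Step 2: the instructions side by side.**

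| | Table 9 | Table 11 |
|---|---|---|
| Class of cimetidine | moderate | weak |
| Class of tipranavir/ritonavir | strong | weak |
| General instruction | avoid; use an alternative | caution |
| DLT window, escalation cohorts | not allowed | no bar stated |
| Venetoclax dose, cimetidine | cut by 50% in that cycle; 3-day wait before the initial dose | no rule |
| Venetoclax dose, tipranavir/ritonavir | withheld in that cycle; 7-day wait before restart | no rule |
| Washout before study treatment | 7 days | none stated |

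**Step 3: is there another explanation for the double listing?** Four other drugs appear in Table 11 and in a restrictive table, but for different properties:

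- aprepitant: moderate inhibitor in Table 9, weak inducer in Table 11;
- dronedarone: moderate inhibitor in Table 9, P-glycoprotein inhibitor in Table 11;
- amiodarone: CYP2C8 substrate in Table 8, weak CYP3A inhibitor and P-glycoprotein inhibitor in Table 11;
- fexofenadine: OATP1B1/3 substrate in Table 10, P-glycoprotein substrate in Table 11.

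These entries record separate interactions and are not misclassified. For cimetidine and tipranavir/ritonavir the property is CYP3A inhibition in both tables, so no second interaction accounts for the listing.

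**Step 4: which table governs?** The body text attaches its restriction and its washout to the medicines listed in Table 9. Both drugs are listed there by name. The Table 11 instruction asks for caution and lifts no restriction. Read together, the text puts both drugs under Table 9. This is an inference; no sentence states it.

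**Step 5: which drug is realistic?** Section 4.1.2 excludes patients with a known HIV-positive history and requires testing at screening when status is unknown, where local rules permit. If tipranavir/ritonavir is taken to be an HIV treatment (an assumption, since the documents give no indication for it), its use here is unlikely. Ritonavir alone also has its own line in the strong column of Table 9 and none in Table 11. Cimetidine remains.

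**The case against.** The strongest reply is that the obligations do not conflict. Table 9 binds by drug name, and caution under Table 11 can be observed at the same time. A site goes wrong only if it overlooks Table 9. Other safeguards make that less likely: the Sponsor reviews eligibility before each enrolment (Section 4.2), all concomitant medicines are recorded (Section 4.4), and sites are told to consult prescribing information. This largely stands, and it is why the point is minor. It does not remove the wrong label, and none of these safeguards says which class applies.

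A reader might infer three stronger things that the documents do not support.

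- **That the protocol permits full-dose venetoclax with these drugs, or that DLT data are compromised.** The Table 9 restriction applies by name. The documents give neither the frequency of use nor the size of any change in exposure, and the DLT-window bar concerns escalation patients only, not the approximately 80 planned for expansion.
- **That the problem covers all six drugs shared between Table 11 and a restrictive table.** Four of the six are listed for different properties and belong where they are.
- **That a blanket rule applying the strictest instruction across Tables 8 to 11 would be a purely clerical repair.** Bosentan and rifampin are inducers in Table 9, where footnote c leaves a route after the DLT window with Medical Monitor guidance. Section 1.3.2.1 also contemplates inducer use after that window and names rifampicin. Table 10 prohibits both drugs, subject to its half-life footnote. A blanket rule would close the footnote c route, which is a clinical decision.

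**Conclusion.** The inconsistency is real but minor. Two drugs carry two CYP3A-inhibitor classes in Section 4.4.2 with materially different venetoclax instructions, and one of them, cimetidine, is likely to matter in practice. Table 9 is the natural governing rule. The remaining risk is that a site consults Table 11 alone, or reads the Section 4.1.2 criterion with the Table 11 class in mind.

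No effect on venetoclax exposure, toxicity or DLT rate can be computed, and none is claimed. No endpoint, sample size or decision rule is shown to be affected. The conclusion rests on the two tables as extracted, and on taking the body text to apply Table 9 by name. The documents do not establish which class is pharmacologically correct. Keeping the Table 9 class is the cautious default, for the sponsor to confirm when editing.

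**What to change.** Delete cimetidine and tipranavir/ritonavir from the weak CYP3A inhibitor column of Table 11, leaving the Table 9 entries as they are. Optionally, add a sentence to Section 4.4.2 stating that a drug listed both as a CYP3A inhibitor in Table 9 and in Table 11 follows Table 9. That sentence would also cover aprepitant and dronedarone.

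Keep the aprepitant, dronedarone, amiodarone and fexofenadine entries in Table 11. Leave bosentan and rifampin (Table 9 footnote c against Table 10) to a separate clinical clarification by the sponsor.

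The cost is two deleted entries and at most one sentence in the next amendment, with no effect on sample size, endpoints or visits.

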#### **4.4.3 Additional Restrictions**

Use of the following foods is prohibited during the study and for at least 3 days before initiation of study treatment:

- Grapefruit
- Grapefruit juice
- Products that contain grapefruit
- Seville oranges (including marmalade that contains Seville oranges)
- Star fruit

#### **4.5 STUDY ASSESSMENTS**

Please see [Appendix 1](#) and [Appendix 2](#) for the schedules of activities performed during the study.

##### **4.5.1 Informed Consent Forms and Screening Log**

Written informed consent for participation in the study must be obtained before performing any study-related procedures. Informed Consent Forms for enrolled patients and for patients who are not subsequently enrolled will be maintained at the study site.

All screening evaluations must be completed and reviewed to confirm that patients meet all eligibility criteria before enrollment. The investigator will maintain a screening log to record details of all patients screened and to confirm eligibility or record reasons for screening failure, as applicable.

Results of standard-of-care tests or examinations performed prior to obtaining informed consent, and within the defined window, may be used as screening and baseline assessments (see [Appendix 1](#) and [Appendix 2](#)); such tests do not need to be repeated for screening purposes (e.g., screening tumor assessment).

Study treatment should be initiated within 28 days after the Informed Consent Form has been signed. Those patients who fail screening based on longer waiting times for certain results or due to study technical reasons (such as cohort on hold) can be rescreened once at a later date if they were deemed eligible before the screen failure. The decision to rescreen individual patients will be made jointly by the Roche Medical Monitor and the investigator and any other person the investigator or Medical Monitor considers necessary to assist with this decision. Any such decision and the reasons for

it will be clearly documented. Any out-of-window assessments need to be repeated and undergo a complete review by the Roche Medical Monitor.

#### **4.5.2 Medical History and Demographic Data**

Medical history includes clinically significant diseases, surgeries, reproductive status, smoking history, and alcohol and drug abuse. In addition, all medications (e.g., prescription drugs, over-the-counter drugs, herbal or homeopathic remedies, nutritional supplements) used by the patient within 14 days prior to the screening period will be recorded.

Demographic data will include age, sex, and self-reported race/ethnicity.

The following clinical parameters relative to disease history, diagnosis, and prognostic indices will be recorded at screening:

- Date of initial diagnosis
- ECOG performance status (see [Appendix 7](#))
- Ann Arbor staging (see [Appendix 8](#))
- For patients with FL: FLIPI and FLIPI2 (see [Appendix 9](#))
- For patients with DLBCL: IPI (see [Appendix 9](#))
- B symptoms (unexplained fever >38°C, night sweats, and unexplained weight loss > 10% of body weight over 6 months)
- Previous lines of anti-lymphoma treatment as well as response to prior therapy, date of disease progression in relation to start date of prior treatment, and date of last dose of prior treatment

